#### *Increasing Awareness:*

The first section of the GC tailored website exhibits the "What" of HIV and STI testing. The first subsection, "The Facts," presents a grid of STI facts in a random order. The final box is a list of seven questions participants can ask a provider during a testing visit. These questions were developed by the GC youth and community advisory boards, and were found to be helpful to pilot trial participants when they encountered test counselors who weren't perceived to be effective. The second subsection, "STIs," displays boxes that contain the names of specific STIs. Once clicked, pop-up content presents information specific to that STI including what kind of infection it is, how it can be contracted, possible symptoms, testing options (e.g., oral swab versus blood draw), and treatment options (if applicable). The third subsection "Tests," displays boxes with information on the different types of tests for STIs (e.g., blood test, saliva test, swab test). Once clicked, pop-up content presents information on what STIs each type of test can test for, and the specific steps taken to administer the test and contains general prevention facts (e.g., "You won't always know if someone has an STI.") relevant to this population.

*Promoting self-appraisal and increasing motivation for engaging in prevention services:* The second section of the GC tailored website, the "Why," encourages participants to assess their motivations, values, and strengths regarding HIV/STI testing. Reasons for getting tested are tailored to participants' testing history (e.g., "Never tested" versus "Tested for HIV, but not STIs") in order to acknowledge their prior behaviors. Building on best practices, persuasive messages regarding the importance of linking to prevention services are presented by linking participants' values to the desired outcomes. GC then reinforces behavioral (e.g., having tested between follow-up assessments) and cognitive aspects of HIV prevention services that participants expressed confidence in doing (e.g., asking a partner to get tested before having sex) based on baseline or follow-up assessments.

*Acknowledging and Overcoming Barriers:* The third section of the GC tailored website, the "How," explores barriers (e.g., financial costs, social norms, and prioritization) to participants' desire to get tested for HIV/STIs, as well as how their strengths and social support systems can help them make a choice about testing. Recognizing that barriers and supports may shift over

time, the pages' content is tailored based on the most recent responses to questions in the follow-up assessments. This way, GC can address current barriers, provide strategies on how to overcome them, and current supports, with suggestions for how to utilize them.

#### *Linking Users to Culturally-Sensitive Providers:*

The final section of the GC tailored website, the "Where," contains a listing of local testing sites and filtering options (e.g., visit can be 30 minutes or less, site is open on weekends, site prescribes PrEP). Testing sites are rank-ordered using an algorithm that accounts for each site's average mystery shopping scores regarding the site's LGBTQ inclusivity and confidentiality during the testing process, providers' LGBTQ friendliness, discussion of sex and relationship goals, ability to discuss motivations for testing, sex positive tone, avoidance of making assumptions about the client, assessment of potential intimate partner violence, and pressure to adopt risk reduction strategies. Participants can choose to send specific site information to themselves via email or text message.

Primary objective:

- **Phase 1a: Populating the Sites**

We will create a master list of the HIV/STI testing sites and employ our mystery shopper methodology to examine the quality of HIV test counseling and local HIV/STI testing sites in the 3 trial cities (Houston, Philadelphia, and Atlanta). Data will then be entered into our existing GC test locator console. During the first 3 months of the project, we will train research assistants to identify existing HIV/STI locations and PrEP providers across the three cities. Following a sequential method, research assistants will compile an exhaustive list using the local health department HIV testing site directory. They will then triangulate the information obtained through CDC's National Prevention Information Network (NPIN) with HIV/STI testing and PrEP providing locations using Google search. Emory has collected a list of PrEP provider registries already and worked with NASTAD (National Alliance of State and Territorial AIDS Directors), Kaiser Family Foundation and UCSF (University of California, San Francisco) to launch a national provider registry in summer 2016, which is available and updated as necessary for this project. We will then verify the information obtained by calling the clinics and verifying their HIV/STI testing hours, services provided, phone numbers, addresses, language used to describe clients and services, targeted client age, and cost of services. Once this information is reconciled, sites' information will be entered into the open-source GC console. Agency characteristics are used to sort sites based on their geographic area, operating hours, ability to test without an appointment, proximity to public transportation, and insurance or ID requirements.

- **Phase 1b: Recruitment and eligibility for RCT**

Using 2014 American Community Survey data about the racial/ethnic distribution of children under the age of 18, we propose to sample a racially/ethnically diverse sample of YMSM that parallels the racial/ethnic distribution in each city. We will use geographically targeted ads on sites including Facebook, Tumblr, Instagram, Reddit, and Twitter.

- **Phase 1c: Data Collection and Retention for RCT**  
We will use SurveyGizmo to collect YMSM's data. *At baseline, participants will be logged into the SurveyGizmo assessment by site study staff. For follow-up assessments, participants will receive a unique link which will allow them to complete the surveys in multiple sittings or to resume a survey that has timed out or been closed.* Online surveys allow participants to complete the survey at a convenient location, circumvent barriers (e.g., scheduling, transportation) present in interviewer-administered or phone-based interviews, and decrease social desirability. To maximize completion rates, participants will receive email and/or text reminders that a survey is available. Although we will employ recommended strategies to avoid loss to follow-up, we project a conservative attrition of 20%. In the pilot study, we achieved >80% retention using the approaches proposed here.

Secondary objective:

- **Phase 2a: Enrolling and Training of Mystery Shoppers**  
We will enroll and train 10-15 mystery shoppers per city to conduct the mystery shopper assessments. This approach follows best practices indicating that youth involvement is vital when designing relevant and appropriate HIV interventions for the target population. As study staff, we will work with the ATN site in each city to enroll HIV-negative YMSM (ages 18-24) who are interested in serving as mystery shoppers. We will employ a stratified purposive sampling strategy to ensure age and racial/ethnic diversity across mystery shoppers. Of the 10-15 mystery shoppers in each city, we will attempt to recruit diversity in age and race/ethnicity. Mystery shoppers will be 18 to 24 years old (inclusive).
- **Phase 2b: Site Visits**  
Based on feedback from agency directors in our original study, we will send all agency directors a letter informing them of their site's selection for the study before the mystery shopper visits and contact information to reach the research PIs if they have questions about the procedures. Shoppers will be instructed to report that they do not have income or health insurance and do not possess any proof of identification. In so doing, we will be able to ascertain whether these would be potential barriers to testing at a given location and determine the lowest possible fees that would be charged to a YMSM.
- **Phase 2c: Integration of Scores into GC Console**  
We will enter the 10 domain scores from the mystery shopping evaluations for each site into our GC administrative console, hosted online, and accessible to the study team for maintenance (e.g., if a testing location changes its hours of operation or closes). The rating criteria are not meant to establish an absolute measure of each site, but rather a rating that may then be used relative to an individual's stated needs and desires for his testing experience. An average between the composite site score and the user's stated values will be used to rank a provided list of local HIV/STI testing sites.

Tertiary objective:

- **Phase 3a: Randomly Select 10 Sites from Each City**

We will randomly select 10 sites from Philadelphia, Houston, and Atlanta to carry out semi-structured qualitative in-depth interviews with the agency's director.

*Eligibility Criteria for Site Directors:*

- Speak and read English
  - Site director of an HIV/STI testing site
  - The testing site is located in Philadelphia, Atlanta, or Houston
- **Phase 3b: In-Depth Interviews**

The interviews (60-90 minutes) will focus on 4 domains: (1) existing prevention services used and/or promoted by the agency, (2) agency (internal) resources currently missing, that if identified and addressed, could improve delivery of HIV/STI and PrEP services to YMSM, (3) feedback on the biannual evaluation assessments and their use for service-delivery improvements, and (4) the advantages and disadvantages of GC rollout within ASOs. We will interview providers via teleconference in a private office at the University of Pennsylvania to maximize candidness and privacy while decreasing travel-related costs. We will use BlueJeans, a simple and low cost alternative that requires no server infrastructure to set up or maintain and allows providers to be HIPAA-compliant. University of Pennsylvania holds the BAA for this BlueJeans license. The site directors will not be compensated for their participation in these interviews.

### 3.2 Study Population

For the primary objective, we plan to recruit a diverse sample of 15-24 year olds. Of the 480 participants, we propose that 98 (20%) will be non-Hispanic white men, 232 (48%) will be non-Hispanic black men, 122 (25%) will be Latino men, 22 (5%) will be non-Hispanic Asian-Pacific Islanders, and 6 (2%) will be other non-Hispanic or multi-racial men. Transgender participants are excluded in this protocol as the intervention has not been adapted to meet the needs of transgender youth.

Eligibility criteria will include the following: Individuals who were assigned male at birth and currently identify as male, 15-24 years old (inclusive), self-report as HIV-negative or sero-status unaware, speak and read English, live in Philadelphia, Houston, or Atlanta, and meet one or both of the following high risk criteria: have not received HIV testing in past six months and/or report having consensual anal sex with a man in the past six months.

For the secondary objective, we plan to recruit a diverse group of 10-15 mystery shoppers per city. Mystery shoppers will be 18 to 24 years old (inclusive).

Eligibility criteria will include the following: Individuals who were assigned male at birth and currently identify as male, 18-24 years old (inclusive) at time of screening, self-report as HIV-negative, speak and read English, live in Philadelphia, Houston, or Atlanta, are able to travel to and from HIV/STI testing sites, report same-sex attraction, and have access to internet via a computer or smartphone.

For the tertiary objective, we will randomly select 10 testing sites per city who participated in the mystery shopper perspective and conduct a semi-structured qualitative in-depth interview with the site's director.

Eligibility criteria will include the following: Individuals who are site directors of an HIV/STI testing site in Philadelphia, Atlanta, or Houston, and who can speak and read English.

### 3.3 Sample Size

For the primary objective, the research activities involve enrolling a sample of 480 HIV negative or status unaware YMSM (15-24 years), with the aim of maintaining a randomized sample of approximately 400 online-recruited YMSM over 12-months.

For the secondary objective, the research activities involve enrolling a sample of 30-45 HIV negative YMSM (18-24 years), with the aim of visiting each city's public testing sites twice - two mystery shoppers will visit each testing site (i.e., the same shopper will not go to the same testing site twice).

For the tertiary objective, the research activities involve enrolling a sample of 10 HIV testing site directors per city, with the aim of conducting a semi-structured qualitative in-depth interview.

### 3.4 Study Randomization, Stratification, or Description of Non-Random Assignment Procedures

For the primary objective, participants will be randomly assigned to one of two groups, stratified by city/SRV site: intervention and control. After consent, YMSM are randomized to either the control or intervention condition (Intervention, n=240; Control, n=240). **We intend to blind participants to the intervention arm assignment in order to improve the internal validity of the study, the rigor of the assessment of outcomes, and to minimize bias due to awareness of treatment assignment.**

For the secondary objective, mystery shoppers will visit testing sites that have been randomized such that each site has an equal likelihood of being shopped on any given day at any given time (during normal operating hours).

For the tertiary objective, participants will be randomly selected from participating HIV testing sites in each of the three cities. Only sites that have been visited and assessed by study participants will be included in each city's sample for randomization.

## 4.0 ELIGIBILITY AND SCREENING

### 4.1 Primary Objective (RCT): Inclusion Criteria

- *Assigned male sex at birth and currently identifies as male*

- *Aged 15 to 24 years (inclusive) at time of screening*
- *Self-report as HIV-negative or sero-status unaware*
- *Speak and read English*
- *Not be on PrEP at time of enrollment*
- *Report having consensual anal sex with a male partner in the prior 6 months and/or report having not received HIV testing in prior 6 months*
- *Reside in Philadelphia, Houston, or Atlanta*
- *Access to internet*

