The primary assessment for a difference between intervention arms for 'frequent tester' rates will be a two-sided Z-test for independent proportions with pooled variance. Confidence intervals (95%) will also be reported for the observed difference between the GC and control arms in 'frequent tester' rates. The same analysis plan described above will be used for the other primary outcomes that as binary (i.e., STI testing, PrEP awareness).

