## **5.3 Randomization Procedures**

For the primary objective, after consent, YMSM are randomized to either the control or intervention condition, stratified by city/SRV site (Intervention, n=240; Control, n=240). Participants will be randomized on a 1:1 basis to either the control or intervention arm.

For the secondary objective, testing sites are randomized by day of the week and time of day. After consent and training, participants will work with study staff to find day and time slots for their site visits.

For the tertiary objective, 10 eligible testing sites in each city will be randomly selected. The site director for those sites will be contacted for an interview.

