### 6.1.2 On-study Evaluations/Measures

- *HIV Testing:* Follow-up surveys will repeat the HIV testing questions in each follow-up survey. The HIV testing outcome will be: the proportion of MSM tested for HIV two or more times at least 3 months apart in the 12-month follow-up period (“frequent tester”). As an additional analysis, we will also examine the proportions of participants who receive one HIV test.
  - Among self-reported newly diagnosed HIV+ cases, we will measure their linkage and engagement with appropriate medical care after initial diagnosis using criteria employed in prior ATN protocols with youth. We will define linkage as an HIV-related medical visit within 45 days of referral, and engagement as a second HIV-related medical visit within 16 weeks of initial visit. Onset of ART initiation, self-reported adherence to ART, and viral suppression are exploratory indicators, as we recognize that our follow-up period may not be a sufficient amount of time to see these changes.
- *STI Testing:* The STI testing outcome is defined as the proportion of YMSM tested for STIs at least once in the 12-month follow-up period. We will ask participants what STIs they have been tested for, the anatomic sites where they were tested, the date of their most recent STI test (if known), and whether a medical provider had diagnosed them with an STI. In the follow-up surveys, we will ask participants whether they had been tested for STIs in the past 3 months (for the 1-month follow-up survey, we ask about the past 30 days). If STI testing is reported, we will ask participants to indicate what tests they received, and whether they were diagnosed with an STI by a medical provider.
- *PrEP Use:* At each follow-up assessment, PrEP-eligible HIV-negative YMSM (per CDC guidelines) will be asked whether they have begun using PrEP. We will also ascertain if a provider recommended PrEP and/or were offered a prescription for PrEP.
 

*Site Evaluations:* Across both trial arms, YMSM who report testing in the prior 3 months will complete self-evaluation forms of their testing experiences to assess comfort, quality, and concerns after visiting a site for HIV/STI testing and PrEP prevention services. The assessment form is the same form used by the mystery shoppers. We will use these data to update the WebApp and to send aggregate data of YMSM's satisfaction with services to agencies biannually.

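### The frequent-tester comparison ignores HIV testing before enrolment and the city strata: the Z-test is valid, but it gives up precision that an adjusted analysis could recover at little cost

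*Combined protocol and SAP*

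**What the plan says.** Entry (protocol section 4.1): a participant must report recent anal sex with a male partner "and/or report having not received HIV testing in prior 6 months". A man tested last month therefore qualifies through recent anal sex alone.

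Allocation (sections 3.4 and 5.3): 1:1, "stratified by city/SRV site: intervention and control". City/SRV site is the only stratification factor named.

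Outcome (section 6.1.2, repeated in 10.2): "the proportion of MSM tested for HIV two or more times at least 3 months apart in the 12-month follow-up period", called the frequent tester. It is one yes/no value per man for the whole follow-up.

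Analysis (section 2.4, binary outcomes): the main assessment of frequent-tester rates is a "two-sided Z-test for independent proportions with pooled variance", with a 95% confidence interval for the difference. No covariate or stratum is mentioned.

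Other places where prior testing could enter:
- The GEE in section 2.4 has arm, time and their interaction as its only predictors.
- The adjusted regressions in section 10.1 list socio-demographics, substance use, psychological distress and process data, but not testing history.
- Section 10.3 adjusts for baseline values in the analysis of having tested at least once, which is a different endpoint. Its mixed model has a covariate term whose contents are not named.

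**The concern.** Whether a man was tested in the 6 months before enrolment plausibly predicts whether he tests twice in the next 12. The entry rule guarantees that this status can vary between participants, and the trial collects testing history. The plan itself adjusts a related endpoint for baseline values. Leaving prior testing out of the frequent-tester comparison means that variation between the two kinds of men stays in the standard error, although an adjusted analysis would remove it. City, which was used to randomise, is also left out.

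At stake is the efficiency of the test on which the sample size was based. There is little slack: section 10.2 requires at least 400 men, while 480 enrolled with the 20% attrition projected in section 3.1 leaves 480 × 0.8 = 384.

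**Working it through.** **Inputs from the documents.** Two-sided alpha 0.05, 80% power, 400 participants, 13-point difference (section 10.2); 1:1 allocation (section 5.3).

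**Inputs assumed, because the documents give none.** The share of recent testers, and the frequent-tester rate in each group.

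**1. The plan's own figure.** For two proportions with pooled variance, n per arm = [1.96·√(2p̄(1−p̄)) + 0.8416·√(p₁(1−p₁) + p₂(1−p₂))]² / 0.13². With an assumed control rate of 25% (38% under GC, p̄ = 0.315) this is (1.2876 + 0.5474)² / 0.0169 ≈ 199.2, so 200 per arm and 400 in total. At 30% the total is 430, and at the worst case of 43.5% it is 464. The control rate is not stated, so 400 can be matched but not confirmed.

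**2. Unadjusted test.** Take control 35%, GC 48%, 200 per arm. Null SE = √(2 × 0.415 × 0.585/200) = 0.0493. Alternative SE = √((0.35 × 0.65 + 0.48 × 0.52)/200) = 0.0488. Power = Φ[(0.13 − 1.96 × 0.0493)/0.0488] = 75.3%.

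**3. Adjusted test.** Half the men are recent testers and the effect is 13 points in both groups. For control rates of 50% and 20% (GC 63% and 33%), the within-group variances average 0.205 (control) and 0.2271 (GC). Alternative SE = √(0.4321/200) = 0.0465; null SE = 0.0469. Power = Φ[(0.13 − 1.96 × 0.0469)/0.0465] = 79.3%. The variance falls by 1 − 0.4321/0.4771 = 9.4%.

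| Control rates, recent testers / others | Gap | Variance cut | Power, unadjusted → adjusted |
|---|---|---|---|
| 40% / 30% | 10 | 1% | 75.3% → 75.8% |
| 45% / 25% | 20 | 4% | 75.3% → 77.1% |
| 50% / 20% | 30 | 9% | 75.3% → 79.3% |
| 60% / 10% | 50 | 26% | 75.3% → 86.8% |

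The pattern does not hinge on the half share. With 70% recent testers, power rises from 74.2% to 77.5% at the 30-point gap. With 30% recent testers and rates of 60% and 10%, it rises from 80.1% to 89.9%.

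**4. Chance imbalance is the same loss seen another way.** The SD of the between-arm difference in the share of recent testers is √(2 × 0.25/200) = 5.0 points. An imbalance above 10 points in either direction has probability 4.6%. At a 30-point gap, a 1-SD imbalance moves the arm difference by 0.30 × 5.0 = 1.5 points, and (1.5/4.88)² = 9.4%, exactly the variance cut in step 3.

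**5. Type I error, by simulation** (200,000 trials, 200 per arm, stratified by prior testing only). Overall, the Z-test rejects in 5.0% to 5.2% of null trials. In the roughly 2.5% of trials with at least 10 points more recent testers in the GC arm, it rejects in 5.1%, 6.8%, 10.1% and 20.3% for gaps of 10, 20, 30 and 50 points. A Cochran-Mantel-Haenszel test stays at 4.3% to 5.1% in those same trials.

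**The case against.** The strongest reply is that nothing is broken. Randomisation makes the Z-test valid, and its standard error already contains the variation from chance imbalance. That stands. A reader might infer that the primary result is biased or its false-positive rate inflated. The documents do not support this, and the simulation shows overall type I error at about 5%. Nor are imbalance and noise two separate harms (step 4).

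A reader might also infer that prior testing must be known for everyone before allocation, because eligibility depends on it. Under the and/or rule it need not be. A man who reports recent anal sex is eligible whatever his testing status, so a screener could skip the item for him. The screener is named in section 4.9, but its questions are not in the documents. Testing history is documented only in the baseline survey (section 6.1.1), which is completed after randomisation (section 5.1).

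The size is unknown. One test in the past 6 months is a crude proxy for later frequent testing, and at a 10-point gap the gain is negligible. This stands too, which is why a range is given.

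The mixed model in section 10.3 includes baseline as a time point and targets change, and section 2.4 names the arm-by-time interaction as the primary overall hypothesis test. That is fair for the repeated measures, but it does not reach the frequent-tester comparison, which has one value per man.

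Finally, the entry rule is deliberate, and section 3.1 tailors content to testing history, so prior testers are an intended audience. That they have little room to improve, or dilute the effect, is conjecture.

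**Conclusion.** The point holds as one of efficiency. The plan enrols men with different recent testing behaviour, and compares frequent-tester rates without using that difference or the city strata. The planned test remains valid. Adjustment would add roughly 0.5, 2, 4 or 11 power points for gaps of 10, 20, 30 or 50 points, and would protect against a misleading answer in the few badly imbalanced trials. These figures assume a 13-point effect that is the same in both groups, 200 per arm, half recent testers and a 35% control rate. The shares and rates are assumptions, not figures from the documents. The effect of ignoring city was not quantified. The entry rule itself needs no change.

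**What to change.** Before unblinding, amend section 2.4 so that the main analysis of frequent-tester rates is a Mantel-Haenszel risk difference with 95% confidence interval, stratified by city and by HIV testing in the 6 months before enrolment (yes/no). Keep the unadjusted Z-test as a sensitivity analysis.

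Name the source of the testing status. Use the screener if every participant was asked the item. Otherwise use the HIV testing history in the baseline survey, which follows randomisation but comes before participants are helped onto the WebApp (section 5.1). In that case, confirm that the survey dates the last HIV test closely enough to derive the 6-month status, since the protocol mentions a date only for the last STI test.

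Adding the status to the allocation strata is optional. It is possible only if the screener records it for all participants and enrolment is still open. Effects within each status group may be reported as exploratory: with an even split each would rest on about 100 men per arm.

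The cost is a change of analysis wording and six analysis strata (3 cities × 2). If either existing source holds the status, no new data are needed. The choice must be fixed in advance, because adjustment chosen after an imbalance has been seen would not be credible.
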